12.0 Vulnerable Populations

12.1 If the research involves individuals who are vulnerable to coercion or undue influence, please describe additional safeguards you will include to protect their rights and welfare. Consider the applicable items listed below:

- *If the research involves Virginia Tech students, indicate whether these are students of any of the investigators. If so, describe whether the activities will take place during class time as part of the curriculum and the steps you will take to reduce the possibility that students feel obliged to participate in order to improve their course grade. The HRPP can provide further guidance as needed. Describe whether you will request access to student records (e.g., SAT, GPA, GRE scores).*
- *If the research involves employees of Virginia Tech or the research sponsor, describe steps you will take to ensure that the employees are freely participating and describe how their data will be protected from inspection by their supervisors.*
- *If the research involves Virginia Tech NCAA athletes, you must obtain approval from the athletic department.*
- *For research involving Montgomery County Public Schools, you must obtain county approval (after obtaining contingent Virginia*

Tech approval). Other locales have different requirements; please check on these and describe here. Approval is typically granted by the superintendent, principal, and classroom teacher (in that order). Approval by an individual teacher is insufficient. School approval, in the form of a letter or a memorandum should be uploaded as a supporting document.

- *If the research involves pregnant women, review “CHECKLIST: Pregnant Women (HRP-412)” to ensure that you have provided sufficient information in this protocol.*
- *If the research involves prisoners, review “CHECKLIST: Prisoners (HRP-415)” to ensure that you have provided sufficient information in this protocol.*
- *If the research involves persons who have not attained the legal age for consent to treatments or procedures involved in the research (minors), review the “CHECKLIST: Minors (HRP-416)” to ensure that you have provided sufficient information in this protocol.*
- *If the research involves cognitively impaired adults, review “CHECKLIST: Cognitively Impaired Adults (HRP-417)” to ensure that you have provided sufficient information in this protocol.*

Virginia Tech Students might participate in the study if they meet the inclusion criteria, although students will not be directly recruited because of their status. However, no students that have had or have any relationship with this lab will be included. Pregnant individuals will not be included in this study.

13.0 Number of Subjects

13.1 Indicate the total number of subjects to be enrolled and how this number was determined (e.g., sample size calculation [show], number of available subjects in a finite pool, number of tests funding award would allow):

In this study, we require n=90 (N=100 accounting for 10% attrition) participants to complete the study when using repeated measures with three groups and two measurements per participant.

Our sample sizes are based on a repeated-measures within-between interaction ANOVA design using medium effect size ($f=0.25$) and 95% power. To account for multiple testing, we will control for five comparisons in each experiment; therefore, we use an alpha of 0.01.

We have been successfully recruiting cigarette smokers in our community for the past 10 years. Based on our experience with prior studies, we anticipate that 10% of participants don't complete the study.

22-432 Effects of narratives on demand for low and high ventilated cigarettes and substitution for alternative products.

13.2 If this is a multi-site study, indicate the number of subjects to be enrolled at this site and the total to be enrolled from all sites:

N/A

13.3 If applicable, indicate the number of potential subjects you expect to screen for enrollment, and the number of subjects you will need to complete the research procedures:

As stated previously, we have developed and are currently using a separate pre-screening protocol, which occurs prior to enrolling participants into our research protocols. As described above, we anticipate enrolling 100 participants to complete a total of 90 participants.

13.4 If the study has more than one procedure, indicate the total number of subjects to undergo each procedure separately:

All participants will undergo all three sessions unless they withdraw consent.

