2.0 Objectives

2.1 *Describe the purpose, specific aims, or objectives of this study:*

Purpose: To compare the effects of narratives on demand for low and high ventilated cigarettes and substitution for alternative products in the Experimental Tobacco Marketplace.

2.2 *State the hypotheses to be tested:*

22-432 Effects of narratives on demand for low and high ventilated cigarettes and substitution for alternative products.

The primary hypothesis is that narratives will decrease purchases of ventilated cigarettes and increase purchases of alternative products compared to the control narrative (fact sheet).

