4.0 Study Design and Statistical Analysis Plan

4.1 *Describe the basic study design/approach (e.g., qualitative study using five focus groups of first year students to describe assimilation into the university community; randomized controlled trial of a behavioral change intervention to increase dietary intake of whole grains; pre- post-test evaluation of new pedagogical techniques to improve adult literacy):*

In a between-group within-subject repeated measures design, participants will be randomized to one of three groups (narrative, fact sheet, or control) and complete five ETM conditions, which include six trials assessing different cigarette prices: a) high-ventilated cigarette alone, b) low-ventilated cigarette alone, c) high- and low-ventilated cigarette with high-ventilated cigarettes increasing in price, d) high- and low-ventilated

22-432 Effects of narratives on demand for low and high ventilated cigarettes and substitution for alternative products.

cigarette with low-ventilated cigarettes increasing in price, and e) usual, high- and low-ventilated cigarette with usual cigarettes increasing in price.

4.2 *Describe corresponding data analysis plan/approach (e.g., content analysis of focus group transcripts; descriptive analysis followed by linear regression modeling; nonparametric analysis of pre- and post-test measures):*

A within-between subject analysis of variance (ANOVA) will test for differences in substitution and demand measures between groups (narrative, fact sheet, and control) and condition (e.g., high-ventilated cigarettes alone). We will test for the interaction between group and condition, suggesting a difference in how each group responds to different conditions. Order effects will be included in all models to account for the balanced Latin square design for counterbalancing the ETM conditions within the session. We will perform post-hoc contrasts to compare groups, based on our hypothesis.

Additional analyses might be conducted.

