For the sampling phase, participants will be provided two days worth of study cigarettes based on their number of cigarettes smoked per day, half of high-ventilated cigarettes and half of low-ventilated cigarettes. Participants will also be provided with a sample of other commercially available tobacco product to try. Participants will be instructed the order in which to use the products on the next three days. The order will be counterbalanced across participants.

During the sampling phase, participants will receive text messages asking how many of each product they sampled during those days.

2) Before the ETM session, participants will be randomized to the narrative, the fact sheet or the control group. In the ETM session, they will listen to a recording of a narrative of an individual who quit tobacco products or a fact-sheet with overall rates of smoking and its negative consequences. Participants in the control group will not be exposed to any recording. Then, participants will buy tobacco products to use throughout the next 7 days. Participants will complete a total of 30 purchasing trials each for 7 days' worth of products. They will be exposed to 5 conditions with cigarettes increasing in price. A balanced Latin square design will be used to present the following conditions: a) a) high-ventilated cigarette alone, b) low-ventilated cigarette alone, c) high- and low-ventilated cigarettes with high-ventilated cigarettes increasing in price, d) high- and low-ventilated cigarettes with low-ventilated cigarettes increasing in price, and e) usual, high- and low-ventilated cigarettes with usual cigarettes increasing in price. Additionally, participants will complete the Questionnaire on Smoking Urges-Brief, the Product Evaluation Scale, questions about the cigarette harshness, items of the Transport Narrative Questionnaire (narrative and fact sheet groups only), the Positive and Negative Affect Schedule

22-432 Effects of narratives on demand for low and high ventilated cigarettes and substitution for alternative products.

(narrative and fact sheet groups only), a manipulation check and an open-ended question about the recording they listened (narrative and fact sheet groups only), and the Experiment/Experimenter Attitudes Rating Scale.

For the seven days following the ETM session, participants will be asked not to use or purchase any outside tobacco/nicotine products and not to sell or give away any of their purchases.

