**NCT: NCT05487625**

**Document date: 09/13/2022**

### ***Study Design and Statistical Analysis plan***

In a between-group within-subject repeated measures design, participants will be randomized to one of three groups (narrative, fact sheet, or control) and complete five ETM conditions, which include six trials assessing different cigarette prices: a) high-ventilated cigarette alone, b) low-ventilated cigarette alone, c) high- and low-ventilated cigarette with high-ventilated cigarettes increasing in price, d) high- and low-ventilated cigarette with low-ventilated cigarettes increasing in price, and e) usual, high- and low-ventilated cigarette with usual cigarettes increasing in price.

A within-between subject analysis of variance (ANOVA) will test for differences in substitution and demand measures between groups (narrative, fact sheet, and control) and condition (e.g., high-ventilated cigarettes alone). We will test for the interaction between group and condition, suggesting a difference in how each group responds to different conditions. Order effects will be included in all models to account for the balanced Latin square design for counterbalancing the ETM conditions within the session. We will perform post-hoc contrasts to compare groups, based on our hypothesis.

Additional analyses might be conducted.

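### The 95% power in Protocol 13.1 belongs to a three-group, two-measurement interaction; it is neither the planned five-condition test nor the narrative-versus-fact-sheet comparison that the hypothesis needs

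*Protocol*

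**What the plan says.** Protocol 13.1 gives the basis for the sample size: "Our sample sizes are based on a repeated-measures within-between interaction ANOVA design using medium effect size", f = 0.25, 95% power, and "repeated measures with three groups and two measurements per participant". On multiplicity it says "we will control for five comparisons in each experiment; therefore, we use an alpha of 0.01", without listing the five. The result is 90 completers, or 100 enrolled with 10% attrition.

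The design is larger than that basis. Protocol 7.2 says of participants: "They will be exposed to 5 conditions with cigarettes increasing in price". The SAP has them "complete five ETM conditions, which include six trials assessing different cigarette prices". Neither document says which two measurements 13.1 means.

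The hypothesis in Protocol 2.2 is that "narratives will decrease purchases of ventilated cigarettes and increase purchases of alternative products compared to the control narrative (fact sheet". It sets narrative against fact sheet and covers two outcomes. The third arm, which hears no recording (7.2), does not enter it. The endpoint item (3.4, under Study Endpoints) names substitutability and compares two groups, without saying which two of the three.

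The analysis in Protocol 4.2 is an ANOVA that "will test for differences in substitution and demand measures between groups (narrative, fact sheet, and control) and condition". The SAP repeats it and adds "We will test for the interaction between group and condition, suggesting a difference in how each group responds to different conditions". Group comparisons are left to post-hoc contrasts tied to the hypothesis. Their groups, outcome, conditions and alpha are not given.

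**The concern.** One power figure is stated, and a reader will take it as the chance of confirming the hypothesis. Two mismatches prevent that.

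First, 13.1 enters two measurements where the analysis has five. This changes the degrees of freedom and the noncentrality. It also brings in sphericity, which cannot fail with two measurements but can with five. The plan names no correction.

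Second, the omnibus interaction and the hypothesis are different questions. The interaction can be significant because the no-recording arm differs while narrative and fact sheet behave alike. Conversely, a narrative effect of equal size in every condition adds nothing to the interaction and shows only in the group main effect.

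What is at stake is the reading of the result. After a null or positive finding on narrative versus fact sheet, nobody could say from the plan what difference the trial was able to detect, or on which measure.

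**Working it through.** **Inputs.** From 13.1: k = 3 groups, m = 2, f = 0.25, alpha = 0.01, N = 90. From 4.1, 7.2 and the SAP: five conditions. Assumed, because the documents do not give them: equal arms of 30, within-person correlation ρ, sphericity epsilon ε, and any difference between two arms.

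**Step 1. The plan's own figure.** For the within-between interaction, λ = ε f² N m/(1−ρ), with df ε(k−1)(m−1) and ε(N−k)(m−1).
- m = 2, ρ = 0.5: λ = 0.0625 × 90 × 2/0.5 = 22.5 on 2 and 87 df; power 95.7%.
- 90 is the smallest equal-arm total that reaches 95% (87 gives 94.9%).
- ρ = 0.3: λ = 16.07; power 84.5%. Power reaches 95% at ρ = 0.484.
- Enrolment: 90/0.9 = 100.

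So 13.1 reproduces, provided ρ is about 0.48 or more.

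**Step 2. The same test with five conditions** (ρ = 0.5, f = 0.25, alpha 0.01; at ε = 1, λ = 0.0625 × 90 × 5/0.5 = 56.25 on 8 and 348 df).

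| ε | Power |
|---|---|
| 1 | over 99% |
| 0.75 | 99.7% |
| 0.5 | 97% |
| 0.25 (lowest possible) | 78% |

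Power drops below the two-measurement figure when ε is under about 0.45. Without a correction the type I error is affected too: in a simulation with no true effect and ε between 0.40 and 0.54, the uncorrected interaction test rejected 4% to 6% of the time at a nominal 1%.

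**Step 3. What 13.1's own effect implies for narrative versus fact sheet.** With two measurements the interaction is a comparison of change scores. On that scale f becomes 0.25 × √(2/(1−ρ)) = 0.5 at ρ = 0.5. The check is 0.5² × 90 = 22.5, the same λ as in step 1. This f is the spread of three group means, so the gap δ between two of them, in change-score SDs, depends on their arrangement. The noncentrality is δ√(30/2), and the two-sided 1% critical t on 87 df is 2.634.

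| Arrangement | δ | Noncentrality | Power |
|---|---|---|---|
| Narrative and fact sheet are the extremes, third arm midway | 2 × 0.5 × √1.5 = 1.22 | 4.74 | 98% |
| Only one of these two arms differs | 0.5/√(2/9) = 1.06 | 4.11 | 93% |
| Equally spaced, these two adjacent | 0.5 × √1.5 = 0.61 | 2.37 | 40% |
| These two act alike | 0 | 0 | no more than alpha |

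At ρ = 0.3 the first three become 91%, 80% and 27%.

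**Step 4. If the contrast is instead averaged over five conditions.** This is an illustration only, since the documents give no two-arm difference. The SD of a participant's mean is √((1 + 4ρ)/5) = √0.6 = 0.775 single-condition SDs at ρ = 0.5. A difference of 0.5 single-condition SD is then 0.5/0.775 = 0.645 SD of the averaged measure. Its noncentrality is 2.50 and its power 45% at alpha 0.01. If 0.5 SD refers to the averaged measure itself, the noncentrality is 1.94 and power is 25%. The difference detectable with 80% power is 0.90 SD of the analysed measure, or 0.90 × 0.775 = 0.70 single-condition SD.

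**The case against.** The best defence is that the calculation is sound and, if anything, cautious. It reproduces at a conventional correlation of 0.5, and adding conditions with the same f raises interaction power unless sphericity fails badly. That stands for the omnibus interaction. It says nothing about the contrast, where the arrangement of the three means moves power from 98% to alpha at the same f.

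A second defence is that the plan does provide for contrasts and ties them to a hypothesis fixed in advance, while 3.4 points to substitutability and to a two-group comparison. This also stands in part. A reader might infer that the contrast will be picked after seeing the data; the documents do not say so, and the tie to the hypothesis counts against it. What remains is that the contrast is not defined. Section 2.2 has two outcomes, 3.4 has one and does not name its two groups, and 4.2 analyses substitution and demand measures.

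A third objection is that the 0.5 SD difference comes from outside the documents. It does, and so do the correlations. The mismatch between 13.1 and the design, and the absence of a power statement for the hypothesis, rest on neither.

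**Conclusion.** The point holds as an inconsistency in the power basis and a gap in specification. 13.1's two measurements contradict the five conditions of the design and SAP. Its 95% applies to the omnibus interaction on two measurements, with a correlation of about 0.48 or more. It is not the power of the planned five-condition test (over 99% down to 78% at correlation 0.5, according to epsilon), nor of narrative versus fact sheet (98%, 93%, 40% or no more than alpha under 13.1's own f, with 30 per group, two measurements, correlation 0.5 and alpha 0.01).

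A reader might go further and infer that 90 completers are too few. The documents do not support that: several arrangements give power near or above 95%, and the plan states no two-arm difference against which to judge the number. The matter should be fixed before analysis, but it does not call the sample size itself into question.

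**What to change.** 1. In Protocol 13.1, replace the two measurements with those actually analysed, or name the two that are meant. State the assumed within-person correlation. Say that the 95% refers to the omnibus interaction. Add the power, or the detectable difference with its SD scale, for narrative versus fact sheet at 30 per group.
2. In Protocol 4.2 and the SAP, make narrative versus fact sheet the planned primary contrast in place of an undefined post-hoc one. Give its outcome, reconciling 2.2 with 3.4 and naming the two groups in 3.4. Give its alpha. Give the conditions it uses, restricted to those in which the outcome can be measured: purchases of high-ventilated cigarettes, for example, cannot be averaged over a condition that offers only low-ventilated ones.
3. Keep the group-by-condition interaction as a separate test over the five conditions, with a sphericity correction such as Greenhouse-Geisser, or fit a mixed model with unstructured covariance.

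The cost is wording in three places and minor analysis work, with no added participants. The sponsor should expect the stated power for the hypothesis to be less favourable than 95%.

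### The five comparisons are handled with a per-test alpha of 0.01, naturally read as single-step Bonferroni; Holm's step-down keeps the same 5% family-wise error and n = 90 and never rejects less

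*Protocol*

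**What the plan says.** Multiplicity is mentioned once, in Protocol section 13.1 (Number of Subjects): "To account for multiple testing, we will control for five comparisons in each experiment; therefore, we use an alpha of 0.01". The sample size there rests on a within-between interaction ANOVA with three groups and two measurements, "using medium effect size ($f=0.25$) and 95% power". It gives 90 completers, or 100 enrolled after 10% attrition.

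The analysis text, worded alike in Protocol section 4.2 and the SAP, describes the ANOVA, the group-by-condition interaction and the follow-up contrasts: "We will perform post-hoc contrasts to compare groups, based on our hypothesis". It gives no alpha and no multiplicity procedure. The five comparisons are not listed in either document, and the 5% family-wise level is implied by 5 × 0.01 but not stated.

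Protocol section 2.2 predicts effects in two directions at once: "narratives will decrease purchases of ventilated cigarettes and increase purchases of alternative products".

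**The concern.** A flat threshold holds every comparison to 0.01 even after others in the family have been rejected. A step-down rule relaxes the threshold as rejections accumulate, with no loss of error control. The hypothesis predicts fewer purchases of one product type and more of another, so the plan itself expects more than one true effect, and that is when a step-down rule helps.

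At stake is a misleading pattern of results. The trial could report that the narrative moved one purchase measure or condition and not another, when the second missed only the single-step threshold and would have passed the step-down one.

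**Working it through.** **1. Reproduce the sizing.** Inputs from Protocol 13.1: f = 0.25, k = 3 groups, m = 2 measurements, alpha = 0.01, power 95%. The correlation between measurements is not given; rho = 0.5 is assumed.

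- Noncentrality: lambda = f² × N × m/(1 − rho) = 0.0625 × 90 × 2/0.5 = 22.5.
- Degrees of freedom: (k − 1)(m − 1) = 2 and (N − k)(m − 1) = 87.
- Power at N = 90 and alpha 0.01 is 95.7%. The smallest N reaching 95% is 88, or 90 in equal groups.
- Enrolment: 90/0.9 = 100.

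The plan's figures reproduce at alpha 0.01. The assumed rho matters: the required N in equal groups is 105 at rho 0.4 and 72 at rho 0.6, so only a value of about 0.5 gives 90. At alpha 0.05 the same formula needs only 66, so 0.01 was the level used.

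**2. Error control.** Five tests at 0.01 have a family-wise error of at most 5 × 0.01 = 0.05, or 1 − 0.99⁵ = 0.049 if independent. Holm compares the ordered p-values with 0.05/5, 0.05/4, 0.05/3, 0.05/2 and 0.05 (0.01, 0.0125, 0.0167, 0.025, 0.05) and stops at the first failure. Every threshold is at least 0.01, so anything the flat rule rejects, Holm rejects too. The 5% bound holds under any dependence.

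**3. Power of one interaction test at N = 90 at each Holm step:** 95.7%, 96.4%, 97.2%, 98.1% and 99.1%. The first step is 0.01, so the sizing does not move.

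**4. Gain when all five effects are real.** Simulation of five two-sided equicorrelated normal tests, 400,000 trials per case. The correlations are assumptions.

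| Per-test power at 0.01 | Correlation | Average power, flat → Holm | All five found, flat → Holm |
|---|---|---|---|
| 95% | 0.5 | 95% → 98% | 83% → 95% |
| 80% | 0 | 80% → 90% | 33% → 67% |
| 80% | 0.5 | 80% → 88% | 51% → 75% |
| 80% | 0.8 | 80% → 86% | 63% → 81% |

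At 80% per-test power, the gain in finding all five falls from 34 points (67 − 33) at correlation 0 to 24 at 0.5 and 18 at 0.8.

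**5. The same comparison with the plan's own kind of test.** Five interaction F tests at N = 90, 20,000 runs per case.

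| f | Real effects | Correlation between tests | Mean power per test, flat → Holm | All real effects found, flat → Holm |
|---|---|---|---|---|
| 0.25 | 5 | 0 | 95.8% → 99.0% | 80.7% → 95.4% |
| 0.25 | 5 | 0.5 | 95.8% → 98.7% | 85.2% → 96.1% |
| 0.25 | 3 | 0 | 95.8% → 97.2% | 87.9% → 91.9% |
| 0.25 | 3 | 0.5 | 95.7% → 97.0% | 89.6% → 92.9% |
| 0.25 | 1 | 0 or 0.5 | 95.7% → 95.7% | same |
| 0.20 | 5 | 0 | 79% → 90% | 31% → 66% |
| 0.20 | 5 | 0.5 | 79% → 87% | 49% → 74% |

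Simulated family-wise error under Holm at f = 0.25 was 4.1% to 5.1%, consistent with the 5% bound within simulation error.

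**The case against.** The strongest reply is that the documents do not commit the analysis to a flat rule. The 0.01 stands only in the sample-size section, no method is named, and sizing at 0.01 is also what Holm would require. This stands in part: a reader might infer that the plan fixes 0.01 for every test at analysis, and the text does not say so outright. But the section gives 0.01 as the way the five comparisons are controlled, and nothing elsewhere points to a step-down, so single-step Bonferroni is the natural reading. If Holm was intended, the same sentence settles it.

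Second, the family is undefined. The five could be conditions, outcomes or contrasts, and no five-test procedure can be run until they are named. This stands fully and is built into the fix.

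Third, a reader might infer that the loss is greatest because the same people are measured under five conditions. The figures show the reverse: correlation between tests reduces Holm's advantage. What favours Holm is several true effects.

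Fourth, a reader might infer that any real effect with p between 0.01 and 0.05 would be recovered. Holm allows 0.05 only for the last remaining test. With two left the smaller p-value must reach 0.025, and with three 0.0167.

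Fifth, at the stated power the gain per test is small, the chance of at least one rejection is unchanged, and finding all five effects is not an objective in either document. All of this is correct and limits the weight of the point.

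**Conclusion.** The concern holds as a cheap improvement to a valid rule. There is no inflation of error, the sample size is not wrong on this account, and the documents do not support a claim of large power loss at the design effect size. There the benefit is about 3 points per test if all five effects are real, mostly seen in the chance of finding several or all of them, and essentially nothing if one is real. It becomes substantial only if per-test power is lower than planned, for example near 80%, and several effects are real.

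That Holm never rejects less, at the same family-wise error, needs no assumption. The sizes rest on the assumed correlation between the tests, on the number of real effects and, for the F-test figures, on rho = 0.5 between measurements. None of these is given in the documents.

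**What to change.** Keep alpha = 0.01 for sizing in Protocol 13.1. List the five comparisons there and in the SAP, and add after the list: *These five comparisons will be tested with Holm's step-down procedure at a family-wise alpha of 0.05, and Holm-adjusted p-values will be reported.* In the SAP this belongs after the sentence on post-hoc contrasts; Protocol 4.2 carries the same text and should match.

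The cost is a short list and one sentence in each place, with no extra data and no change in N. The list should be fixed before the results are seen. The one drawback is that Holm-adjusted p-values have no equally simple matching simultaneous confidence intervals; Bonferroni 99% intervals can still be shown beside them, on the understanding that an interval may include zero for a comparison that Holm rejects.
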